5.2.2 Secondary Endpoints

The secondary endpoints are as follows:

- MACE within 30 days
- AEs of interest: bleeding events, infusion reactions, hypersensitivity reactions, thrombotic events (including stent thrombosis), frequency of abrupt vessel closure (AVC), transient ischemic attack, redo of stent procedure (revascularization), or emergency coronary artery bypass grafting (CABG)
- Minor bleeding events (BARC Type 2)
- General AEs including change from baseline abnormal safety laboratory test results
- ACT, aPTT, PT, TT, FIB, INR
- PA and correlation with PK

- Thrombolysis in myocardial infarction (TIMI) flow
- Percentage of patients who achieve $ACT \geq 200$ sec
- PK of MT1002

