In $\leq 1/6$ pat lab values preventing dose escalation such as LFT up by $\geq 2 \times$ from baseline; platelet count < 50,000; QTcF interval > 500 ms or > 60 ms change from baseline, based on ECGs; or study drug related vital sign changes that require stabilization of hemodynamics with positive inotropes	Lab values preventing dose continuation such as LFT up by $\geq 2 \times$ from baseline; platelet count < 50,000; QTcF interval > 500 ms or > 60 ms change from baseline, based on ECGs; or study drug related vital sign changes that require stabilization of hemodynamics with positive inotropes	In $\geq 2/6$ pat lab value preventing dose escalation such as LFT up by $\geq 2 \times$ from baseline; platelet count < 50,000; QTcF interval > 500 ms or > 60 ms change from baseline, based on ECGs; or study drug related vital sign changes that require stabilization of hemodynamics with positive inotropes	In $\leq 1/6$ pat lab values preventing dose escalation such as LFT up by $\geq 2 \times$ from baseline; platelet count < 50,000; QTcF interval > 500 ms or > 60 ms change from baseline, based on ECGs; or study drug related vital sign changes that require stabilization of hemodynamics with positive inotropes	In $\geq 3/6$ pat lab values preventing dose escalation such as LFT up by $\geq 2 \times$ from baseline; platelet count < 50,000; QTcF interval > 500 ms or > 60 ms change from baseline, based on ECGs; or study drug related vital sign changes that require stabilization of hemodynamics with positive inotropes

Abbreviations: AE, adverse event; ACT, activated clotting time; BARC, Bleeding Academic Research Consortium; ECG, electrocardiogram; LFT, liver function test; pat, patient; QTcF, QT interval corrected by Fridericia's formula; SAE, serious AE.

The decision on dose escalation/de-escalation/stopping or continuation for the patient cohort will be taken by the Study Management Group based on data review of each dose group considering safety, efficacy, drug concentration, and in conjunction with the prespecified criteria.

End of Cohort 1 SMG meeting held on March 23, 2023 recommended to proceed to cohort 3 if patients in cohort 2 shows insufficient anticoagulation effect. Insufficient anticoagulation effect is defined when 3 patients or more treated within cohort 2 dosing regimen experienced at least one ACT<200 seconds and confirmed by Ad Hoc SMG meeting.

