7.2 Exclusion Criteria

Individuals meeting any of the following criteria at Screening are ineligible to participate in this study:

1. Cardiogenic shock or prolonged cardiopulmonary resuscitation (CPR).
2. Active bleeding, bleeding diathesis, coagulopathy.
3. Any history of intracranial bleeding or structural abnormalities (intracerebral mass, aneurysm, arteriovenous malformation [AVM]).
4. Prior transient ischemic attack, prior stroke within 6 months.
5. Index MI is STEMI (ST elevation Myocardial Infraction).
6. The following planned procedures within 30 days after enrollment: CABG, valve surgery, or additional invasive procedures.
7. Requirement for oral anticoagulants before Day 7 post IP treatment.
8. Based on investigator's discretion, subject is at high bleeding risk, i.e., CRUSADE (Can Rapid risk stratification of Unstable angina patients Suppress ADverse outcomes with Early implementation of the American College of Cardiology/American Heart Association [ACC/AHA] Guidelines) bleeding risk score >60.
9. Suspected aortic dissection.
10. History of gastrointestinal or genitourinary bleeding within the previous 3 months.
11. Refusal to receive blood transfusion if needed during the study.
12. Major surgery in the last month.
13. History of heparin-induced thrombocytopenia and bleeding diathesis.
14. Severe uncontrolled hypertension, defined as a systolic blood pressure > 180 mmHg and diastolic blood pressure > 100 mmHg up to 24 hours of adequate treatment.
15. Prior (within 30 days prior to enrollment) or planned administration of thrombolytics, glycoprotein IIb/IIIa inhibitors, bivalirudin, or fondaparinux for the index MI. Subcutaneous injections of unfractionated heparin and low molecular weight heparin are allowed up to 4 hours and 8 hours, respectively, before study drug. Use of intravenous unfractionated heparin may be continued up until the time of enrollment (just prior to PCI), if ACT is < 200 seconds.
16. Known relevant hematological deviations: hemoglobin (male) < 11 g/dL hemoglobin (female) < 10 g/dL, hematocrit < 35%, platelet count < 100,000 cells/ μ L.
17. Use of Coumadin derivatives and/or Factor Xa inhibitor drugs within the last 7 days.

18. Chronic therapy with non-steroidal anti-inflammatory drugs (NSAIDs; except aspirin) (NSAID use is defined as chronic if these medications are taken more than three times a week for more than three months), cyclooxygenase (COX)-2 inhibitors within 1 month before screening.

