19. Known malignancies or other comorbid conditions with life expectancy < 1 year that may result in protocol noncompliance.
20. Known severe liver disease (i.e., aspartate aminotransferase [AST], alanine aminotransferase [ALT] > 3 × ULN).
21. Known positive serology for hepatitis B & C, HIV screen.
22. Known chronic kidney disease with estimated glomerular filtration rate (eGFR) < 30 mL/min and/or dialysis.
23. Known allergy or intolerance to aspirin, clopidogrel, ticagrelor, prasugrel, bivalirudin, UFH, P2Y12 antagonists, or contrast.
24. Previous enrollment in this trial.
25. Inability to fully cooperate with the study protocol.
26. Any other medical or psychiatric condition that in the Investigator's judgment precludes participation in the study.

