14.4 Safety Analysis

All reported AEs will be coded using the Medical Dictionary for Regulatory Activities (MedDRA), version used will be the current one at the time of analysis. The incidence of TEAEs

This document is confidential.

(events with onset dates on or after the start of the study drug) will be included in incidence summary tables. Events with missing onset dates will be included as treatment-emergent. If a patient experiences more than 1 occurrence of the same AE, the occurrence with the greatest severity and the closest association with the study drug will be used in the summary tables. The major bleeding events, minor bleeding events, MACE within 30 days, and AEs of interest will be summarized by MedDRA system organ class and preferred term, and by cohort and overall; SAEs and AEs causing study discontinuation will also be summarized. All AEs will be listed by patient, along with information regarding onset, duration, relationship and severity to study drug, action taken with study drug, treatment of event, and outcome.

Clinical laboratory data and vital signs will be summarized using descriptive statistics, including mean values and mean change from baseline values, as well as numbers of patients with values outside limits of the normal range at each time point.

12-lead ECGs will be summarized descriptively. The noteworthy QTcF interval (>450 , >480 , >500 msec) and noteworthy change from baseline (>30 and >60 msec) will also be summarized.

Summary tables will be provided for concomitant medications initiated during the study period.

Physical examination results will be listed.

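### Section 14.4 does not show how many patients develop a new or worse laboratory abnormality, or how many reach the Table 1 liver and platelet limits

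*Combined protocol and SAP*

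**What the plan says.** Section 14.4 summarizes clinical laboratory data with descriptive statistics, "including mean values and mean change from baseline values", and adds a count: "as well as numbers of patients with values outside limits of the normal range at each time point". It names no shift table, no count of new or worsened values, and no liver or platelet category. For ECG it does set categories: "The noteworthy QTcF interval (>450 , >480 , >500 msec) and noteworthy change from baseline (>30 and >60 msec) will also be summarized".

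Table 1 in Section 6.1 puts laboratory and ECG limits in one row. The row starts with LFT at least twice baseline and continues: "platelet count < 50,000; QTcF interval > 500 ms or > 60 ms change from baseline, based on ECGs". On that row, at most 1/6 patients allows the dose to continue or rise, 2/6 or more means de-escalation, and 3/6 or more stops the study.

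Section 7.2 lets patients enter out of range. Criterion 20 excludes only "Known severe liver disease (i.e., aspartate aminotransferase [AST], alanine aminotransferase [ALT] > 3 × ULN", and criterion 16 excludes "hematocrit < 35%, platelet count < 100,000", so milder abnormality is admitted. Under Section 11.5 the reference ranges come from local laboratories.

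The primary objective (Section 5.1.1) is to find the safe and well tolerated dose. Section 5.2.2 lists as a secondary endpoint "General AEs including change from baseline abnormal safety laboratory test results".

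**The concern.** The planned count and the dose criterion measure different things. Section 14.4 asks whether a value lies outside a local range at one visit. Table 1 asks whether a patient has changed by a given ratio from baseline (LFT) or crossed an absolute limit (platelets).

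Three features of the count limit its use:

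- It is not restricted to values that are new or worse than at entry. One patient returning to normal cancels another who becomes abnormal.
- It gives a value just out of range the same weight as an extreme one.
- It is made separately at each time point. A result of 1/6 at Day 2 and 1/6 at Day 14 could be one patient or two.

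The trial's main product is a statement that a dose was safe and well tolerated. A reader of the report should be able to check that statement against the plan's own criteria. For QTcF the planned tables allow this; for the laboratory items in the same row they do not.

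**Working it through.** The plan gives no figure on this point. Its one derivable planning figure, 18/(1 - 0.40) = 30 patients screened, reproduces but is not used here. The documents give no normal limits, so I assume an ALT ULN of 35 to 50 U/L and a lower platelet limit of 130,000 to 150,000. All patient values below are invented for illustration. Each cohort has six patients.

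**1. LFT doubling inside the normal range.** ALT values in U/L:

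| Patient | Baseline | Post-dose | Ratio |
|---|---|---|---|
| 1 | 14 | 30 | 2.14 |
| 2 | 16 | 33 | 2.06 |
| 3, 4, 5 | 25, 28, 30 | unchanged | 1.00 |
| 6 | 2.5 x ULN | 2.2 x ULN | 0.88 |

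- Out-of-range count: 1/6 before (patient 6) and 1/6 after (patient 6).
- Mean change: (16 + 17 - 0.3 x ULN)/6. With ULN 35 this is (33 - 10.5)/6 = +3.75 U/L; with ULN 50 it is (33 - 15)/6 = +3.0 U/L.
- Maximum: falls from 87.5 to 77 (ULN 35) or from 125 to 110 (ULN 50).
- Patients at or above twice baseline: 2/6, the Table 1 de-escalation count.

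The minimum rises from 14 to 25, which hints at a shift but does not say how many patients doubled. A low/normal/high shift table would also miss patients 1 and 2, because they stay in the normal category.

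**2. A patient already abnormal who worsens.** One patient goes from 2 x ULN to 4 x ULN and the other five stay normal and unchanged.

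- Out-of-range count: 1/6 and 1/6.
- At or above twice baseline: 1/6.
- Mean change: 2 x ULN/6, that is 70/6 = +11.7 (ULN 35) to 100/6 = +16.7 U/L (ULN 50). The maximum doubles.

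Here the planned summaries do signal that something happened, though the count does not.

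**3. Platelets.** One patient falls from 110,000 to 45,000; the other five are normal and unchanged.

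- Out-of-range count: 1/6 and 1/6.
- Mean change: -65,000/6 = -10,833.
- Below 50,000: 1/6.

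The planned minimum of 45,000 reveals this patient. It would read the same if a second patient were at 48,000, so it cannot separate 1/6 from 2/6, where Table 1 changes its instruction.

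**4. How often a cohort includes someone out of range at entry.** If a proportion p of patients enter out of range on a parameter, the chance of at least one in six is 1 - (1 - p)^6. The documents give no p, so I show a range: p = 5%, 10%, 20% and 30% give 26%, 47%, 74% and 88%. Mixing of old and new abnormality is therefore plausible in cohorts of this size.

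**The case against.** A reader might infer that new laboratory toxicity would be invisible, or that a hidden patient could turn a de-escalation into a continuation. The documents do not support either reading.

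- **Other summaries are planned.** Section 14.4 includes mean change from baseline. Section 14 plans minimum and maximum by dose group and a listing of all data. With six patients per cohort, a listing shows everyone.
- **The adverse event route exists.** Section 11.5 makes any laboratory result that the investigator considers clinically significant an adverse event, and such events reach the incidence tables. The secondary endpoint is itself worded around adverse events.
- **Dose decisions do not run on these tables.** Sections 6.1, 14.7 and 14.8 give them to the Study Management Group, which reviews each cohort's data alongside the Table 1 criteria. Nothing limits it to out-of-range counts. Table 1 also presents its laboratory values as examples.
- **Detail may follow.** Section 14 leaves variable definitions to a later SAP. The Synopsis mentions a category of noteworthy values in a sentence on laboratory data, vital signs and ECG; it could be read to cover laboratory data.

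Most of this stands and limits the consequence, but it does not supply the missing number. Extremes and means do not count patients or show ratios to baseline. The adverse event route depends on judgement, so a doubling within range need not be reported. Rebuilding a prespecified criterion by hand from listings is possible but is not a planned analysis. Section 14.4 defines noteworthy values only for QTcF.

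A reader might also want counts of platelets below 100,000 and of hemoglobin falls of 3 g/dL or more, as further limits from the plan. The first is an entry criterion. The second belongs to the BARC type 3 definition in Table 9, which requires overt bleeding and is already counted in a co-primary endpoint. Neither is a Table 1 laboratory limit.

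**Conclusion.** The point holds as a reporting gap worth closing. The planned laboratory tables give neither the number of patients with new or worsened abnormality nor the number reaching the Table 1 liver and platelet limits. In the illustration the out-of-range count stays at 1/6 while 2/6 patients meet the de-escalation limit. The liver item is the stronger half, because a doubling can occur wholly within range and need not appear in any extreme value. The platelet item is weaker, because the planned minimum reveals at least one patient below 50,000.

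The consequence is for reporting and for checking the safe-dose conclusion. It is not shown that any patient would escape the Study Management Group's review. The illustration rests on assumed patient values and normal limits; the mismatch between what Section 14.4 counts and what Table 1 counts follows from the text alone.

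**What to change.** Keep the planned summaries. Add to Section 14.4 or the SAP, by cohort and overall:

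1. The number of patients with any post-dose LFT at least twice baseline, and the number with any post-dose platelet count below 50,000. State which analytes in Table 6 count as LFT and which pre-dose value is baseline.
2. A patient-level shift table from baseline category (low, normal, high) to worst post-dose category for each laboratory parameter.

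Both are needed: the shift table separates new from pre-existing abnormality, and the limit count catches a doubling within range. Also state whether the Synopsis reference to noteworthy values covers laboratory data.

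The cost is a few extra tables. Table 4 already schedules chemistry at Screening, Day 2, Day 14 and Day 30, and platelet counts before, during and after PCI and at the same follow-up visits. No samples are added and no dosing rule changes.

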14.5 Pharmacokinetic Analysis

The standard PK parameters of peak plasma concentration, area under the curve, elimination half-life, elimination rate constant, volume of distribution, and clearance will be estimated by standard noncompartmental methods.

PK plasma concentrations and PK parameters will be summarized descriptively by cohort.

14.6 Other Analyses

Other endpoints will be summarized descriptively if appropriate. Further analyses will be specified in the SAP.

14.7 Interim Analysis

The study data review after each cohort will be performed by the Study Management Group for decisions on dose escalation, de-escalation, stopping, or continuing for each patient cohort.

The interim analysis is planned in this study. It will be safety, PK, PD and efficacy analyses after getting the clinical data of 9-12 patients.

Further details may be found in the SAP.

14.8 Study Management Group

The Study Management Group (consisting of the Sponsor representatives, the Medical Monitor, one of the principal investigators and an independent cardiologist) will meet to review accumulating safety data after each cohort throughout the study, monitor overall study conduct,

and make decisions regarding the recommended dose for the next patient cohort. A charter will be established to provide decisions of study next step.

15 STUDY MANAGEMENT

15.1 Approval and Consent

15.1.1 Regulatory Guidelines

This study will be conducted in accordance with the accepted version of the Declaration of Helsinki and/or all relevant regulations as set forth in Parts 50, 56, 312, Subpart D, of Title 21 of the US CFR, in compliance with International Council for Harmonisation (ICH) and GCP guidelines and according to the appropriate regulatory requirements in the countries where the study was conducted.

15.1.2 Institutional Review Board/Independent Ethics Committee

Conduct of the study must be approved by an appropriately constituted IEC/IRB. Approval is required for the study protocol, protocol amendments (if applicable), IB, ICFs, recruitment material and patient information sheets, and other patient/subject-facing material.

15.1.3 Informed Consent

For each study patient, written informed consent will be obtained before any protocol-related activities. As part of this procedure, the Principal Investigator or designee must explain orally and in writing the nature of the study, its purpose, procedures, expected duration, alternative therapy available, and the benefits and risks involved in study participation. The patient should be informed that he/she may withdraw from the study at any time, and the patient will receive all information that is required by local regulations and guidelines for ICH. The Principal Investigator will provide the Sponsor or its representative with a copy of the IEC-/IRB-approved ICF before the start of the study.

15.2 Data Handling

Any data to be recorded directly on the eCRFs (to be considered as source data) will be identified at the start of the study. Data reported on the eCRF that are derived from source documents should be consistent with the source documents, or the discrepancies must be explained. See also Section 15.3.

Clinical data will be entered by site personnel on eCRFs for transmission to the Sponsor. Data on eCRFs transmitted via the web-based data system must correspond to and be supported by source documentation maintained at the study site, unless the study site makes direct data entry to the databases for which no other original or source documentation is maintained. In such cases, the study site should document which eCRFs are subject to direct data entry and should have procedures in place to obtain and retain copies of the information submitted by direct data entry. All study forms and records transmitted to the Sponsor must only include coded identifiers such that directly-identifying personal information is not transmitted. The primary method of data transmittal is via the secure, internet-based electronic data capture (EDC) system maintained by

Premier Research. Access to the EDC system is available only to authorized users via the study's internet web site, where a user-unique assigned username and password are required for access.

Any changes made to data after collection will be made through the use of the EDC system. Electronic CRFs will be considered complete when all missing and/or incorrect data have been resolved.

15.3 Source Documents

Source documents are considered to be all information in original records and certified copies of original records of clinical findings, observations, data, or other activities in a clinical study necessary for the reconstruction and evaluation of the study. The Investigator will provide direct access to source documents and/or source data in the facilitation of trial-related monitoring, audits, review by IECs/IRBs, and regulatory inspections.

The Investigator/institution should maintain adequate and accurate source documents and trial records that include all pertinent observations on each of the site's trial patients. Source data should be attributable, legible, contemporaneous, original, accurate, and complete. Changes to source data should be traceable, not obscure the original entry, and be explained if necessary.

15.4 Record Retention

Study records and source documents must be preserved for at least 15 years after the completion or discontinuation of/withdrawal from the study, at least 2 years after the drug being studied has received its last approval for sale, or at least 2 years after the drug development has stopped, and in accordance with the applicable local privacy laws, whichever is the longer time period.

The Investigator agrees to comply with all applicable federal, state, and local laws and regulations relating to the privacy of patient health information, including, but not limited to, the Standards for Individually Identifiable Health Information, 45 CFR, Parts 160 and 164 (the Health Insurance Portability Accountability Act of 1996 [HIPAA] Privacy Regulation). The Investigator shall ensure that study patients authorize the use and disclosure of protected health information in accordance with HIPAA Privacy Regulation and in a form satisfactory to the Sponsor.

15.5 Monitoring

The study will be monitored to ensure that it is conducted and documented properly according to the protocol, GCP, and all applicable regulatory requirements.

Monitoring visits and contacts will be made at appropriate times during the study. The Principal Investigator will assure he/she and adequate site personnel are available throughout the study to collaborate with clinical monitors. Clinical monitors must have direct access to source documentation in order to check the completeness, clarity, and consistency of the data recorded in the eCRFs for each patient.

The Investigator will make available to the clinical monitor all source documents and medical records necessary to review protocol adherence and eCRFs. In addition, the Investigator will work closely with the clinical monitor and, as needed, provide them appropriate evidence that the study is being conducted in accordance with the protocol, applicable regulations, and GCP guidelines.

